2.1. Youth and mobile phone use

The use of mobile phones and other mobile technologies for improving health through research and practice is growing quickly, particularly in areas with difficult-to-reach populations or where the healthcare infrastructure is less developed (Qudrat-Ullah & Tsasis, 2017). In the Kampala Youth Survey 2014, it was noted that nearly half of the youth owned and used phones daily (Swahn, Braunstein, & Kasirye, 2014). The study assessed psychosocial characteristics based on phone ownership and use and found that those who initially owned and used mobile phones were educated, young, wealthy, male and living in urban areas (Swahn et al., 2014). More recently, cell phone use has expanded to include those living in rural areas, the elderly, and those with less resources to an estimated 23 million subscribers in Uganda (UBOs, 2018). In the prior Kampala Youth Survey (2011), 47% of youth reported owning a mobile phone. Ownership did not vary by sex but was more common among youth above 18 years of age. Mobile phone ownership was more common among those who reported taking care of themselves at night, who reported current drug use and who reported trading sex for money, food or other goods.

As the burden of HIV continues to grow among adolescents and youth, mHealth technology could address many of the healthcare needs of YLWH including adherence to HIV medications, retention in care and self-management (Steve Kanters, 2016), which are critical needs for this priority population. mHealth technology could bridge the divide in healthcare delivery in underserved minority groups. Since ownership of a mobile device is common among the youth, use of mHealth can help increase engagement in HIV care (Ippoliti & L'Engle, 2017). Due to the high incidence of HIV among minorities, adolescents and underserved youth, and their reliance on mobile technology, it is imperative to develop health information technology (HIT) tools tailored to the needs of this population (Schnall, Bakken, Brown III, Carballo-Diequez, & Iribarren, 2016; R. Schnall et al., 2016) (Schnall et al., 2015).

Overall HIV incidence in Uganda has been declining since 2010. However, the new HIV infections are disproportionately concentrated among young people. Given high penetration of mobile phone technology, there is growing support for using mobile health (mHealth) programs to reach vulnerable populations (Chang et al., 2011; Chib & Harris). Given that nearly half of youth in

Uganda own or use mobile phones daily, new research is needed to determine next steps for mobile health (mHealth), including the feasibility of using mobile phones for data collection and interventions with this hard-to-reach population (Swahn et al, Aug 2014).

2.2 Acceptability of mHealth in HIV positive population

[figure not shown]
Several studies on the acceptability and feasibility of mHealth in PLWH have been done, but few of these were conducted among YLWH. One study in South Africa examined short message service (SMS) and/or community-based directly observed antiretroviral therapy (cDOT) as interventions to improve ART adherence for preventing mother- to-child HIV transmission. This study showed that SMS and or cDOT are feasible in this setting. However, safe HIV status disclosure to treatment supporters and confidentiality of text messaging content about HIV and ART were deemed to be crucial implementation factors (Nachega et al., 2016).

Few mHealth studies have been conducted among youths despite several studies of mHealth apps (Amith, Loubser, Chapman, Zoker, & Rabelo Ferreira, 2012; Luxton, June, & Chalker, 2015), usability of the devices (Doris Caliz), and negative effects of sexualized video apps (Burnay, Bushman, & Laroi, 2019). Brown et al, conducted 6 focus group discussions to explore adolescent use of mobile technology for meeting their health information needs in Columbia, when given smart phones with mHealth apps. The study assessed health seeking information behavior among adolescents and found that the main motivation for using mHealth app was their performance speed and information needs. Barriers for use of the app included use of non-phone app technology (i.e. phone, books), non-mobile resources (i.e. parents, teachers, siblings), and other health related entities not directly related to the usability of mHealth (Sheehan, Lee, Rodriguez, Tiase, & Schnall, 2012) (Sparkes, Valaitis, & McKibbon, 2012).

Breach of confidentiality may occur following receipt of text messages. In an mHealth study among diabetics in Ethiopia, willingness to receive text messages for appointment reminders was 70.5%, (Jemere et al., 2019). In North West Ethiopia, willingness to receive text message medication reminders among PLWH was only 50.9%, perhaps because use of SMS can't guarantee privacy and participants may have felt it was not safe to receive the mHealth support (Kebede, Zeleke, Asemahagn, & Fritz, 2015). In the rural United States, a survey carried out among 24 respondents, showed a demand for mHealth services, out of the 24 respondents, 63% were in good health, a total of 65% were willing to receive prerecorded messages for appointment reminders

from the doctor (Sankaranarayanan & Sallach, 2014). In rural India, willingness to receive mobile phone reminders for drug adherence was high (98%) among the 479 respondents. Of these, 424 (89%) preferred voice calls alone to other forms of communication (DeSouza, Rashmi, Vasanthi, Joseph, & Rodrigues, 2014).

In a rural Ugandan setting, a cross-sectional study found that over 60% of patients could potentially benefit from a mobile phone-based ART adherence support (Kim et al., 2015). Most of the mHealth studies conducted are SMS studies and only one used IVR. A qualitative study among youth assessed SMS based intervention to improve ART adherence in 2 clinics in Kampala, Uganda. Results suggested improved adherence could be achieved through reminders and social support. However, youth also suggested “intervention logistics related to content, frequency, timing and two-way messages” would be helpful to practitioners in the field (Rana et al., 2015). Another qualitative study in South-Western Uganda nested within sixty-two pilot intervention study participants found that SMS reminders and real-time adherence monitoring led to the habit of adherence, and real-time monitoring was interpreted as “being seen”, “being cared about” which transformed their moods (Ware et al., 2016). In rural Uganda cohort of 276 participants on ART, more than half (64%) possessed a mobile phone and were willing to be contacted after a missed clinic appointment. In 79% of episodes of missed visits, patients presented for refills within a mean duration of 2.2 days (SD = 1.2 days) after mobile phone call reminder (Kunutsor et al., 2010). Another cross-sectional survey among PLWH in rural Uganda assessed the “acceptability of and preferences for text messaging, preferences for laboratory results notification, privacy and confidentiality and cell phone use and literacy”. All the participants expressed interest in the service although they had challenges regarding “interpreting messages, discouragement upon learning bad news, and technical issues” (Siedner, Haberer, Bwana, Ware, & Bangsberg, 2012). In a study of the feasibility, validity, and acceptability of real-time adherence monitoring using a Wise pill wireless electronic adherence monitor (EAM) and self-reported missed doses via interactive voice response (IVR) and short message service (SMS) among 49 adults and 46 children in Mbarara, Uganda, adherence was higher in children than adults (92.8% vs 89.5%) by EAM, and 99–100% for both adults and children by IVR/SMS self-report (Jessica E. Haberer et al., 2013).

2.3 mHealth and ART adherence virological outcomes

Poor adherence to antiretroviral treatment is a public health challenge associated with development of drug resistant strains necessitating initiation of costly second line therapy, and possibility of transmission of drug-resistant HIV by the non-adherent spouse (Chesney, Morin, & Sherr, 2000; De Costa et al., 2010; Paraskevis et al., 2017).

A quasi-experimental cohort study involving 150 HIV-infected individuals from Bangalore, India, showed that among participants on antiretroviral therapy (ART) between April and July 2010, optimal adherence increased from 85% to 91% patients during the intervention period, an effect that was maintained 6 months after the intervention was discontinued ($p=0.016$). Both, IVR calls and SMS reminders were considered nonintrusive and not a threat to privacy. A significantly higher proportion agreed that the IVR was helpful compared to the SMS ($p<0.001$) (Rodrigues et al., 2012).

A systematic review done by Ridgeway K et al, of the peer-reviewed and grey literature published between 2010 and 2015 to identify interventions designed to improve antiretroviral adherence among adults and adolescents in low and middle-income countries, found 43 interventions for adults, 6 involved both adults and adolescents and only 2 were among adolescents (Ridgeway et al., 2018). Two systematic reviews (Caroline Free, 2013; Free et al., 2013) found modest evidence for the benefits of mHealth technology. Both reviews recommended mHealth implementation, but argued that high quality (and adequately powered) clinical trials that measure clinical outcomes are essential (Tomlinson & Rotheram-Borus, 2013).

Garofalo et al, May 2016, conducted a randomized trial of a two-way, personalized daily text messaging intervention to improve adherence to antiretroviral therapy (ART) among 105 poorly adherent HIV-positive adolescents and youth, ages 16–29. The average effect estimate over the 6-month intervention period was significant for $\geq 90\%$ adherence ($OR=2.12$, $95\% CI=1.01–4.45$, $p<.05$) and maintained at 12-months (6-months post-intervention) (Garofalo et al., 2016).

Patient-centered approaches exploiting mobile phone communications (mHealth) have been shown to improve adherence to cART and promote achievement of suppressed HIV plasma viral loads(A. R. Campbell et al., 2018a; J. I. Campbell & Haberer, 2015). A systematic review by H. Anglada-Martine et al, revealed that the use of text messages or mobile applications to enhance adherence to medication do seem to have been beneficial, as 65% of the studies evaluated had

10 FEB 2023

RESEARCH & ETHICS COMMITTEE
Version 3.2, 12th Jan 2022
[name]

positive outcomes. However, they recommended that more high-quality studies be conducted in order to demonstrate whether this type of technology reduces the considerable costs to the health system generated by non-adherence (Anglada-Mart et al., 2017).

During the WelTel Kenya 1 SMS trial, participants who received SMS support had significantly improved ART adherence and rates of viral suppression compared with control participants (Lester et al., 2010). In rural Uganda, text messaging was effective with regard to increasing ART adherence among adults, and this study aims to explore this effect among adolescents with poor virological suppression (A. Musiimenta et al., 2018).

Medication adherence is the “Plus” in the 90-90-90-Plus global challenge, emphasizing the importance of ART adherence in achieving viral suppression. Many gaps remain in meeting these goals, adherence self-efficacy, depression, stressful life events, and perceived stigma were significant predictors of medication adherence (Corless et al., 2017). Mobile phone applications that support treatment adherence address forgetfulness, knowledge gap; an important barrier to treatment adherence, and this needs to be explored among the youths in Uganda.

2.4 mHealth and retention in care

Predictors of poor retention in HIV care include younger age, male sex, racial or ethnic minority status, low socioeconomic status, no usual source of health care, less advanced HIV disease, fewer non-HIV-related comorbidities, and greater unmet psychosocial needs (Giordano, Hartman, Gifford, Backus, & Morgan, 2009). Thus, interventions to improve retention in care should incorporate informational, motivational, and behavioral skill components (Giordano, 2011).

Retaining individuals who have initiated ART in care is challenging. A review by Fox and Rosen 2010, estimated that 20% of patients in resource-limited settings are lost to follow-up within 12 months of initiating therapy (Fox & Rosen, 2010). Prior the era of “test and treat”, the ART naïve “ART-ineligible” patients’ clinic retention rate was estimate at 63% at month 12 (Kohler et al., 2011). There are many challenges for continuity of care, financial constraints, travel difficulties and stigma are factors that can prevent PLWH who start treatment from continuing in care (Mebal Namwabira, 2011).

Many people newly diagnosed with HIV are lost to follow-up shortly before or after timely initiation of antiretroviral therapy. One study in Kenya documented that people living with HIV

felt that increased communication via the text messaging intervention had the potential to enable early identification of problems, leading to timely problem solving that could improve retention and engagement in care during the first year after diagnosis. Engaging PLWH at all points along the cascade of care is essential for transforming the management of the disease from a fatal condition to a chronic one (Edward M. Gardner, McLees, Steiner, Del Rio, & Burman, 2011; Smillie et al., 2014).

[figure not shown]
In a recently published community-based individual randomized trial in Uganda, no statistically significant differences in retention were observed in the first 6 months between those randomized to either mobile-phone or physical contact tracing reminders. Retention was higher among those who received physical contact reminders at month 12 (91.5% versus 82.1%; p=X) (Kiwanuka et al., 2018). Although physical contact tracing reminders had higher retention at 12 and 18 months, mobile technology has several advantages which may be cost saving. The challenges of physical contact included structural barriers, time consuming, health care worker exhaustion and physical infrastructure challenges.

Various studies in Uganda have shown that patient-related factors resulting in loss to follow-up include transportation costs, distance to health centers, inconsistent income and lack of social support. Financing of transport improved retention, but this option is not cost effective nor sustainable in resource poor countries (Emenyonu et al., 2010; Kasigeire, 2014; Tuller et al., 2010).

Mobile health interventions may improve engagement in care. Mobile apps provide a convenient vehicle for reaching a large audience and offer the potential to create personalized and interactive interventions that can be used anonymously and discretely. In a study evaluating how youth use technology and mobile apps and how their use of technology could support their health and influence their engagement in care, participants suggested that a mobile health application should have the ability to connect to a community of other youth living with HIV, readily access healthcare providers, track personal data and information (such as laboratory data), and obtain health news and education (Dillingham et al., 2018).

2.5 mHealth technologies costs

Information systems, such as electronic health records (EHRs) and mobile phones and handheld computers (also called mHealth), can be of enormous value in providing health care in multiple settings. A review done in 2011 showed that with the exception of personal digital

assistant (PDA)-based data collection, there are still few scientifically rigorous data on the effectiveness and cost-effectiveness of e-health systems in developing countries (Blaya, Fraser, & Holt, 2010). The World Health Organization (WHO) published a manual on implementing EHRs for developing countries. The manual states that a thorough cost-benefit analysis should be conducted to compare the options against each other and the costs of any proposed system against the perceived benefits, so as to determine the value of the system to institution/ government (WHO, 2006).

A systematic review of peer-reviewed mHealth literature in Africa published between 2003 and 2013 identified 44 studies on mHealth and found that mHealth interventions were associated with positive health-related outcomes. Their success was based on the accessibility, acceptance and low-cost of the technology, effective adaptation to local contexts, strong stakeholder collaboration, and government involvement. In this review, it was clearly noted that threats such as dependency on funding, unclear healthcare system responsibilities, unreliable infrastructure and lack of evidence on cost-effectiveness challenge mHealth implementation (Blaya et al., 2010).

2.6 Hypotheses and Research Questions

[figure not shown]
1. What is the acceptability of mHealth among YLWH at three (03) of Kiryandongo District HIV Centres, and what are the barriers, facilitators/enablers of ART and clinic visit adherence?

Hypothesis: YLWH will have a high acceptability for mHealth with 70% accepting to use mHealth.

2. What is the effect of the mHealth-CFLU tool on ART adherence among YLWH?

Hypothesis: More than 79% of YLWH using the mHealth-CFLU tool will be adherent to ART (using viral load suppression as a proxy measure for ART adherence we anticipate an increment of 15%).

3. What is the cost of the mHealth CFLU intervention compared to standard of care over a 12 month period?

Hypothesis: mHealth will be cost effective by increasing proportion in care and proportion with viral suppression compared to standard of care

CHAPTER THREE: METHODS

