Adherence to antiretroviral therapy (ART) is the principal determinant for achieving and sustaining viral suppression, which decreases progression to AIDS and reduces risk of mortality (CDC, 1998). Few studies have evaluated mHealth adherence tools among youths in resource-limited settings. This study aims to evaluate whether the CFLU mHealth tool improves ART adherence outcomes among youth receiving ART at a rural hospital in Western Uganda.

Corona virus disease (COVID-19) was first declared in December 2019, in Wuhan city, China. The virus spreads through droplet infection from person to person through sneezing or coughing and contact with contaminated surfaces. The outbreak was announced a Public Health Emergency of International concern on 30th Jan 2020

[figure not shown]
(<https://www.who.int/emergencies/diseases/novel-coronavirus-2019/events>); and declared a global pandemic by World Health Organization on 11th Mar, 2020.
(<https://www.health.go.ug/covid/about-corona-virus>).

General objective:

To assess acceptability, effect and cost of the CFLU mHealth tool on ART adherence and knowledge of COVID-19 among youth initiating and on ART at Kiryandongo District.

Specific Objectives

1a: To assess barriers, enablers of adherence among youth living with HIV in Kiryandongo District at baseline & study end.

- 1b: To assess acceptability of mHealth for HIV adherence support among YLWH in Kiryandongo District at baseline and study end.
- 2: To assess and effect of the CFLU mHealth tool on ART adherence knowledge on COVID-19 among youths initiating or on ART at 6 and 12 months.
- 3: To evaluate the cost of the CFLU mHealth adherence tool in comparison to Standard of Care.

Methods

[figure not shown]
This is a mixed methods sequential explanatory study, with the qualitative study conducted first followed by a randomized control trial and healthcare cost evaluation. The first study is a qualitative study to assess barriers, enablers of adherence and acceptability of mHealth among youths receiving care at three centres in Kiryandongo District. The sample size for this study will be a total of 8 focus group discussions (4 at the study start and 4 at study end) or until data saturation occurs, whichever comes first.

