3.4 Materials and Methods

Study Objectives:

1a: To assess barriers, enablers of adherence among youth living with HIV in Kiryandongo at baseline and study end.

1b: To assess acceptability of mHealth among youth living with HIV in Kiryandongo at baseline and study end.

Study design: Qualitative study with narrative approach

Study purpose: To identify the key behavioral constructs that enable or hinder ART adherence among the youths, and to assess acceptability of mHealth interventions for adherence support.

Study population: YLWH 15-24 years attending Kiryandongo Hospital, Panyadoli Health Centre III or Nyakadote Health Centre II HIV/ART clinic, ART naïve or on ART since Jun 2019.

Sampling: Participants will be purposively selected, each group will include 6-10 YWLH, and there will be a total of 3-5 groups ((Morgan, 1992). The participant groups will comprise of those who are naïve or initiating and on ART since Jun 2019. YWLH will be stratified by age group (≤ 18 ys and > 18 ys) and gender.

Study Procedure:

Selection criteria:

Inclusion: Youth living with HIV, with a documented HIV test result, aged 15-24 yrs, ART naïve or on ART since Jun 2019.

Exclusion Criteria: Youth unable to express themselves verbally, those unable to attend 2 sessions of the discussion

Selection of participants: We shall liaise with the clinic counsellor to refer YLWH aged 15-24 years with a documented HIV test result, patients who are ART naïve or initiating ART and have gone through routine counselling and testing. Stratification by age group and gender will be

[figure not shown]
considered in selection of study participants. Eligible youth will be identified by the clinic counsellor and will be referred to study team which will be located at the HIV clinic. We shall sit one on one with the potential participant, give information about the purpose of the study, and request them to join the focus group discussion on the scheduled date if they agree to take part. This procedure will be repeated until the sample size of a particular group is reached.

Sample Size: Focus group discussions will be held until data saturation is achieved.

Data Collection:

[figure not shown]

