The tool capitalises on a basic mobile phone's core utilities of voice and short messaging services. The system design, development, testing and evaluation was done by Janssen and the Grameen Foundation (<http://motechsuite.org/index.php/implementations>). In 2015, Janssen Global Public Health Research and Development, in close collaboration with the Infectious Diseases Institute Kampala (IDI), developed Call for Life Uganda (CFLU) tailored to the needs of PLHIV in Uganda. The CFLU system follows the Health Insurance Portability and Accountability Act (HIPAA) Privacy and Security rules. While the Privacy rules deals with electronic Protected Health Information, the security rule covers administrative, physical and technical safeguards to ensure confidentiality, integrity and security of electronic protected health information. Data transaction between patient and system is encrypted when it comes to human subjects. The system is password protected, and interaction of system and patient is personalised with a secret code. The system interacts with the patient through a basic mobile phone via a keypad and with the health worker through a web-based interface. The system has options to either use interactive voice response or short message service and the user has to make a choice, get a secret pin code which ensures privacy to enduser.

Screening-Enrolment procedures:

All potential participants will be written on the screening log, and a screening form completed, reasons for screen failure will be documented on the screening log. Following successful screening, the participant will be referred to the Research Assistant (RA) to receive a

thorough explanation of the study so and informed consent is obtained. The RA then administers the stigma questionnaire along with the sociodemographic and medical information, , HIV knowledge and sexual behaviour questionnaires. A client locator form will be completed which will help in physical contact tracing, and the participant will be registered on the enrolment log.

Randomisation will follow (see details of randomisation procedure below) thereafter and the result in the sealed envelope will dictate whether the patient will be registered onto the Call for Life System for the intervention or continue with standard of care as per MoH HIV Management guidelines.

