Continuing IRB Review												
2 nd Amendment – on Study sites												
Study end-line qualitative data collection & Analysis												
Recruitment and follow-up from new sites												
Manuscript write-up first paper- qualitative												
Manuscript write-up second paper												
Manuscript write-up third paper												

[figure not shown]
DHO-District Health Officer

IDI-SRC-Infectious Diseases Institute-Scientific Research Committee

SOM-HDREC-School of Medicine-Higher Degrees Research Ethics Committee

UNCST- Uganda National Council of Science & Technology

v. CFL FGD Guide Youth Study

**Call for Life Youth Study
Focus Group Discussion Guide**

Introduction:

[figure not shown]
Hi, my name is _____ and I want to thank you for joining us today. I am helping to coordinate this study on CFLU system here in Kiryandongo. We are conducting this research to identify barriers and enablers of ART adherence among youths in Kiryandongo District and get views about mHealth interventions; what you like, what you don't like and reasons for liking and not liking the system. I would like to say that there are no right or wrong answers in our discussion. We will simply be discussing your views, opinions and experiences on a range of topics, so please feel comfortable to say what you honestly feel. I would like to tape record the whole session. Please do not be concerned about this, all measures will be taken to maintain confidentiality of the interviews and discussions. Information you tell us will ONLY be used for this research project. As we are tape recording the interview, we ask that you refrain from using names or identifying information of yourself or your partners. If at any time during the interview you feel uncomfortable you can ask for a break, refuse to answer any question, and are always free to leave. Do you have any questions before we start?

Create rapport:

How have you been?

mHealth acceptability among youth

Now that you have received information about mHealth /CFLU, tell us what you know about mHealth/CFLU

1. As a youth, would you accept or refuse to use mHealth CFLU tool?
2. Tell us why you would accept or refuse to use mHealth interventions/ CFLU
3. Can you name the specific elements you would like to help in ART adherence? (Probe on pill reminders, health tips, symptom reporting, use of secret pin)
4. How can the system be used? (Probe on timing - during what hours; frequency)

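### Hypothesis 1 predicts that 70% will accept mHealth, but its only planned source is purposive focus groups, which cannot estimate or test a proportion

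*Combined protocol and SAP*

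**What the plan says.** Section 2.6 pairs the acceptability question with a number: "YLWH will have a high acceptability for mHealth with 70% accepting to use mHealth". It does not say of whom, measured how, or with what precision.

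Acceptability is objective 1b, and section 3.4 gives its design as "Study design: Qualitative study with narrative approach". On sampling it says "Participants will be purposively selected, each group will include 6-10 YWLH, and there will be a total of 3-5 groups". The Abstract instead gives a "total of 8 focus group discussions (4 at the study start and 4 at study end", or fewer if saturation comes sooner. Section 3.4 sets the sample size by saturation: "Focus group discussions will be held until data saturation is achieved". Clinic counsellors refer the participants. The groups are said to be chosen to obtain collective views, and the transcripts go to coding and content analysis.

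The question on acceptance sits in the Focus Group Discussion Guide and is put to the group: "As a youth, would you accept or refuse to use mHealth CFLU tool". No individual tally is described. Acceptability is not among the outcome variables of the randomised trial.

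For the trial, the screening and enrolment text says that potential participants are listed and that "reasons for screen failure will be documented on the screening log". The study explanation and consent follow successful screening. Nothing says that refusals of consent, or their reasons, are logged.

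**The concern.** A hypothesis stated as a percentage needs a defined set of people who were offered the tool, an individual answer from each, and an interval around the result. The planned source has none of these. Members are chosen on purpose, the number of groups follows saturation, and answers are given in front of others. The end-line groups are divided by how much members interacted with the tool, so they hold only youths who already had it.

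At stake is whether the study can say anything about its own first numerical hypothesis. Any percentage drawn from the groups would look like an estimate without being one.

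**Working it through.** **1. The plan's own figure.** There is none for the 70%. The only computed sample size is for the randomised trial: 93 per arm, raised for 10% loss (93 × 1.1 = 102.3, rounded up to 103; 206 in total). Recalculating from 79% against 94%, two-sided 5%, 80% power and continuity correction gives 94 per arm, one away from the plan and of no consequence here. The 206 is used below only as the number enrolled.

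**2. Size of the focus-group sample.** Section 3.4: 3 × 6 = 18 to 5 × 10 = 50 youths. Abstract with the section 3.4 group size: 4 × 6 = 24 to 4 × 10 = 40 per round.

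**3. Best-case precision.** Suppose, generously, that members were a simple random sample answering independently. The 95% half-width at 70% is 1.96 × √(0.7 × 0.3 / n).

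| n | Half-width (points) | Exact 95% interval, count nearest 70% |
|---|---|---|
| 18 | 21.2 | 46.5 to 90.3 (13/18) |
| 24 | 18.3 | 48.9 to 87.4 (17/24) |
| 40 | 14.2 | 53.5 to 83.4 (28/40) |
| 50 | 12.7 | 55.4 to 82.1 (35/50) |

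Section 2.2 cites willingness figures from 50.9% to 98% in other populations. The interval at n = 24 includes the lower of these.

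**4. Dependence within groups.** Answers in one discussion are not independent. The design effect is 1 + (m − 1) × ICC. The ICC is my assumption, 0.1 to 0.4. Four groups of 6 give an effective n of 24/1.5 = 16 down to 24/3.0 = 8. Four groups of 10 give 40/1.9 = 21.1 down to 40/4.6 = 8.7. Half-widths become about 20 to 32 points. Selection bias comes on top, and no interval covers it.

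**5. Individual answers needed.** n = 1.96² × 0.21 / e²: 81 for ±10 points and 323 for ±5.

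**6. What the trial's approach could yield.** The number approached is not in the documents. If 206 enrol and acceptance is a, then N = 206/a, and the half-width is 1.96 × √(a(1 − a)/N).

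| Assumed acceptance | Approached | Half-width (points) |
|---|---|---|
| 50% | 412 | 4.8 |
| 60% | 344 | 5.2 |
| 70% | 295 | 5.2 |
| 80% | 258 | 4.9 |
| 90% | 229 | 3.9 |

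This treats every non-enrolment of an eligible youth as a refusal of the tool. No row is evidence about the true rate.

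**7. Why the reason for refusal matters.** In the 70% row, 295 − 206 = 89 do not enrol. If a share s of them refuse for reasons unrelated to mHealth, acceptance is 1 − 89(1 − s)/295: 69.8% at s = 0, 77.4% at 0.25, 84.9% at 0.5 and 92.5% at 0.75. The estimate moves by up to about 23 points, far more than its sampling error.

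**8. Enrolled over screened is not acceptance.** In the earlier trial of this tool, 600 of 1,031 screened were enrolled (58.2%). At one site 50 of 256 (19.5%) were not enrolled because they had no basic phone or one with a faulty keypad. Such ratios mix eligibility with willingness.

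**The case against.** Hypothesis 1 belongs to the qualitative part. No test, sample size or trial decision depends on the 70%, and the wider research question about acceptability, barriers and enablers suits focus groups well. The baseline guide is said to include structured questions, the end-line guide has a 1 to 5 comfort rating, and call records will be exported for analysis. All of this stands, and it limits the consequence. It does not repair the mismatch: none of these data is tied to the 70%, and comfort among users is not acceptance among those offered the tool.

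Three stronger readings are tempting, and the documents do not support them:

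- **That the existing screening log already supplies the figure at no cost.** As described, it records failures at screening, and consent comes afterwards. Refusals and their reasons would have to be added.
- **That consent to the trial equals acceptance of the tool.** Consent also means accepting randomisation to two arms, one without CFLU, and every participant receives a phone and a transport refund. Youths with hearing loss or unable to use a basic phone are excluded beforehand. Consent is only a proxy.
- **That focus groups must overstate acceptance.** Recruiting youths willing to attend makes this plausible at baseline. But the guide probes refusal and dislikes, and the end-line groups include low users. The bias cannot be quantified, and its direction at study end is not established.

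**Conclusion.** The mismatch holds. The plan states a proportion and assigns to it only a method that cannot estimate or test one. Treated generously as a random sample, the groups would give about ±13 to ±21 points at 70% (±14 to ±18 under the Abstract's count), and about ±20 to ±32 for four groups if the ICC is 0.1 to 0.4. A measure based on everyone eligible and approached could reach about ±4 to ±5 points. That rests on 206 enrolling, on acceptance between 50% and 90%, and on recording why youths refuse.

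A reader might infer that the randomised comparison is weakened. It is not: the trial's outcomes do not use the 70%. The point is confined to Hypothesis 1, where a cheap change would let the study answer what it asks.

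**What to change.** 1. After the tool has been explained and before randomisation, ask each eligible youth approached for the trial one individual question: accept or refuse CFLU. Put it also to those who then decline the trial.
2. Extend the screening and enrolment log to record eligible youths approached, refusals, and whether each refusal concerned mHealth or something else.
3. Report accepted over eligible approached with a 95% confidence interval against 70%, and state beforehand how the comparison will be read. Say that the result applies to youths who met the trial's entry criteria.
4. Report call response in the CFLU arm separately, as uptake. With 103 participants the half-width at 70% is about 8.9 points.
5. Keep the focus groups for reasons, barriers and end-line views, which a log cannot supply. Reconcile the number of groups between the Abstract and section 3.4.

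If this is not wanted, remove the 70% from section 2.6 and present acceptability as qualitative only.

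The cost is one question, added log fields and one descriptive analysis. If only consent is recorded, the result should be labelled a proxy, for the reasons given above.
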